## 2. Study Objectives

### 2.1 Primary Objective – Primary Endpoints

The primary objectives of the study are to evaluate the efficacy and safety of 6 doses of AK002 in subjects with moderate to severe EoD when compared with placebo.

Efficacy will be evaluated by 2 co-primary endpoints:

- 1) First co-primary endpoint- Proportion of Tissue Eosinophil Responders at Week 24:  
A responder is a subject achieving a mean duodenal eosinophil count  $\leq 15$  cells/hpf in 3 highest duodenal hpf
- 2) Second co-primary endpoint- Change in TSS from baseline to Weeks 23–24 as measured by the Patient Reported Outcome (PRO) questionnaire.

The PRO Total Symptom Score (TSS) is comprised of the following 6 symptoms:

- Abdominal pain intensity
- Nausea intensity
- Fullness before finishing a meal intensity
- Loss of appetite intensity
- Bloating intensity
- Abdominal cramping intensity

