#### **4.2.6 Summary Measure of the Estimand**

- Percent (and 95% CI) of subjects having tissue eosinophil response at Week 24 in the AK002 and Placebo treatment groups and the absolute difference (and 95% CI) in the percent response between treatments.
- Least squares mean (LSM) (and standard error [SE]) of change from baseline to the average of Weeks 23–24 TSS and the between treatment difference in the AK002 and placebo treatment groups LSM. LSM and SE derived from mixed model repeated measures (MMRM) model.

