## 6.11.4 Analysis of the Second Co-Primary Endpoint

The second co-primary endpoint will be analyzed using mixed model for repeat measures (MMRM) with treatment, week, treatment-by-week interaction, and baseline TSS-by-week interaction as fixed factors, gender, and baseline TSS (continuous) as covariates, and study site (with pooling by geographic location) as random effect. If the model does not converge with pooled sites as a random effect, it will be simplified with pooled site as a fixed effect.

The weekly TSS score is calculated as the average of the daily TSS scores. Weekly TSS will be set to missing if  $>3$  daily TSS are missing. Baseline TSS score will be the average of the last 2 weeks of daily TSS collected prior to the first infusion. The model variance-covariance matrix will be unstructured. However, if computation does not converge, the matrix will take the form of Toeplitz, autoregressive, or compound symmetry, whichever converges first. A sample of the SAS code for MMRM analysis is provided as below:

```

proc mixed data=tss method=reml;
  class TRTMT USUBJID AVISITN ANALYSIS_CENTER GENDER;
  model CHG= B_TSS TRTMT AVISITN ANALYSIS_CENTER GENDER
  TRTMT*AVISITN B_TTS*AVISITN / DDFM=KR;
  REPEATED AVISITN / SUBJECT=USUBJID (TRTMT) TYPE=UN;
  RANDOM ANALYSIS_CENTER;
  LSMEANS TRTMT*AVISITN / PDIFF CL;
ESTIMATE 'PBO VS. AK002 at WEEKS 23-24' TRTMT -1 1
  TRTMT*AVISITN 0 0 0 0 0 0 0 0 0 0 -1
  0 0 0 0 0 0 0 0 0 0 0 1 / CL;
RUN;

```

Where TRTMT = planned treatment group in numeric (1 = placebo, 2 = AK002); AVISITN = time point (i.e., Weeks 1-2, Weeks 3-4, ..., Weeks 23-24).

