Table 14.1.13a	Baseline Subject Reported Outcome Total and Symptom Scores (MITT Population)
Table 14.1.13b	Baseline Subject Reported Outcome Total and Symptom Scores (Evaluable Population)
Table 14.1.14	Baseline Vital Signs (MITT Population)
Table 14.1.15a	Subject Incidence of Intercurrent Events (MITT Population)
Table 14.1.15b	Subject Incidence of Intercurrent Events (Evaluable Population)
Table 14.2.1.1a	Tissue Eosinophil Responder at Week 24 – Primary and Sensitivity Analysis (Evaluable Population)
Table 14.2.1.1b	Tissue Eosinophil Responder at Week 24 – MITT Population
Table 14.2.1.1c	Tissue Eosinophil Responder at Week 24 – Excluded Population
Table 14.2.1.2.1	Tissue Eosinophil Responder at Week 24 by Gender (Evaluable Population)
Table 14.2.1.2.2	Tissue Eosinophil Responder at Week 24 by Age Group (Evaluable Population)
Table 14.2.1.2.3a	Tissue Eosinophil Responder at Week 24 by Baseline Peripheral Eosinophil Count Subgroup (Evaluable Population)

Table 14.2.1.2.3b	Tissue Eosinophil Responder at Week 24 by Race (Evaluable Population)
Table 14.2.1.2.3c	Tissue Eosinophil Responder at Week 24 by IgE Group (Evaluable Population)
Table 14.2.2.1a	Change from Baseline in Average of Weeks 23-24 PRO Total Symptom Scores – Primary Analysis – MMRM (Evaluable Population)
Table 14.2.2.1a	Change from Baseline in Average of Weeks 23-24 PRO Total Symptom Scores – MMRM (MITT Population)
Table 14.2.2.1c	Change from Baseline in Average of Weeks 23-24 PRO Total Symptom Scores – MMRM (Excluded Population)
Table 14.2.2.2	Change from Baseline in Average of Weeks 23-24 PRO Total Symptom Scores – Sensitivity Analysis 1 – Weekly TSS Due to ICE are Replaced/Imputed Using Placebo-Based Pattern-Mixture Model Multiple Imputation (Evaluable Population)
Table 14.2.2.3	Change from Baseline in Average of Weeks 23-24 PRO Total Symptom Scores – Sensitivity Analysis 2 – Weekly TSS Due to ICE are Replaced/Imputed Using Multiple Imputation by the MCMC Method (Evaluable Population)
Table 14.2.2.4	Change from Baseline in Average of Weeks 23-24 PRO Total Symptom Scores – MMRM (Per Protocol Population)
Table 14.2.2.5.1	Change from Baseline in Average of Weeks 23-24 PRO Total Symptom Scores by Gender – MMRM (Evaluable Population)
Table 14.2.2.5.2	Change from Baseline in Average of Weeks 23-24 PRO Total Symptom Scores by Age Group – MMRM (Evaluable Population)

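### The sample MMRM code for the symptom co-primary has an ESTIMATE labelled Weeks 23-24 that lists 23 coefficients for 24 cells and so returns Weeks 21-22

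*SAP*

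**What the plan says.** SAP 2.1 defines the second co-primary endpoint as "Change in TSS from baseline to Weeks 23–24 as measured by the Patient Reported Outcome (PRO) questionnaire". SAP 4.2.6 gives its summary measure as the least squares mean "of change from baseline to the average of Weeks 23–24 TSS and the between treatment difference", taken from the MMRM. The reporting table, 14.2.2.1a in SAP Appendix 3, is titled "Change from Baseline in Average of Weeks 23-24 PRO Total Symptom Scores – Primary Analysis – MMRM (Evaluable Population".

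SAP 6.11.4 then gives sample `PROC MIXED` code. Treatment is coded 1 for placebo and 2 for AK002, and the coding note reads "AVISITN = time point (i.e., Weeks 1-2, Weeks 3-4, ..., Weeks 23-24", which is twelve periods. The code has two statements that bear on the treatment difference:

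- "LSMEANS TRTMT*AVISITN / PDIFF CL", which prints every pairwise difference between treatment-by-period cells.
- An ESTIMATE labelled as placebo versus AK002 at Weeks 23-24, with treatment coefficients -1 and 1 and the interaction coefficients "TRTMT*AVISITN 0 0 0 0 0 0 0 0 0 0 -1" and then "0 0 0 0 0 0 0 0 0 0 0 1 / CL".

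The same ESTIMATE appears in Step 3 of SAP 6.11.5, for the placebo-based pattern-mixture analysis.

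**The concern.** The label and the coefficients of the ESTIMATE disagree. One zero is missing before the -1, which moves both non-zero weights one period earlier.

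The printed contrast is estimable, so once the misspelled covariate in the MODEL statement is corrected, SAS would return a plausible number under a Weeks 23-24 label. That number would differ from the Weeks 23-24 row of the `LSMEANS` output in the same step. No text says which output row supplies the primary p-value.

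The stake is the symptom co-primary test. Under SAP 5.8, both co-primary tests must succeed before any secondary endpoint is tested.

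**Working it through.** **Cells.** Treatment has 2 levels and `AVISITN` has 12, so the interaction has 2 × 12 = 24 cells. `CLASS` lists `TRTMT` before `AVISITN`, so treatment varies slowest: cell = 12 × (treatment - 1) + period. Placebo is cells 1-12 and AK002 is cells 13-24. Weeks 21-22 is period 11 and Weeks 23-24 is period 12.

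**Coefficients as printed.** The first line has ten 0s and a -1 (11 values). The second has eleven 0s and a 1 (12 values). The total is 23, and the unlisted cell 24 is taken as 0.

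| Position | Weight | Cell |
|---|---|---|
| 11 | -1 | placebo, Weeks 21-22 |
| 23 = 12 + 11 | +1 | AK002, Weeks 21-22 |

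The label's Weeks 23-24 is therefore not reproduced. With eleven 0s, -1, eleven 0s, 1, the weights fall on cells 12 and 24, which are Weeks 23-24 in both arms.

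**Numerical check.** We built the over-parameterised model (intercept, baseline, treatment, period and both interactions with period) and set a known effect of -0.5 × period number. The printed vector was estimable and returned -5.5, the value set for period 11. The 24-value vector returned -6.0, the value set for period 12. Other readings do not rescue the line. With period varying slowest, the printed vector contrasts two placebo cells and is not estimable. With 24 single weeks, it weights placebo Week 11 against placebo Week 23.

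**Days.** SAP Table 2 counts study weeks in sevens from Day 1, so Week *k* runs from Day 7(*k* - 1) + 1 to Day 7*k*. Weeks 21-22 are Days 141-154 and Weeks 23-24 are Days 155-168. Protocol 11.2.1 names Days 155-168 as the critical window. The two do not overlap.

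**Size, if the wrong row were reported.** SD 12.5, 40 per arm and the 7.4-point effect come from SAP 3.5. The correlation ρ between adjacent periods, the other effects and 30 per arm are our assumptions. The true effect is taken as equal in both windows.

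- SE of a treatment difference = 12.5 × √(2/40) = 2.795. At 30 per arm it is 12.5 × √(2/30) = 3.227.
- SD of the gap between the two estimates = √(2(1 - ρ)) × 2.795.
- The probability that exactly one contrast is significant at two-sided 0.05 is taken from the bivariate normal.

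| ρ | 0.7 | 0.8 | 0.9 | 0.95 |
|---|---|---|---|---|
| SD of the gap (points) | 2.17 | 1.77 | 1.25 | 0.88 |
| Effect 7.4, 40 per arm | 0.197 | 0.160 | 0.113 | 0.080 |
| Effect 5.5, 40 per arm | 0.253 | 0.205 | 0.144 | 0.101 |
| No effect, 40 per arm | 0.067 | 0.056 | 0.041 | 0.029 |
| Effect 7.4, 30 per arm | 0.239 | 0.193 | 0.136 | 0.096 |

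A simulation of 2 million draws at 7.4 points and 40 per arm gave 0.197 at ρ = 0.7 and 0.080 at ρ = 0.95. The 5.5-point row lies close to the significance threshold (1.96 × 2.795 = 5.48), so it is near the worst case. The 30-per-arm row is shown because the primary population is the Evaluable subset (SAP 6.1.5) of about 80 patients, so 40 per arm is an upper value.

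**Other faults in the same code.**

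- The MODEL statement has "TRTMT*AVISITN B_TTS*AVISITN / DDFM=KR", but the baseline variable is `B_TSS`. The same misspelling is in 6.11.5.
- `ANALYSIS_CENTER` is in both MODEL and RANDOM. The prose of 6.11.4 makes pooled site random, and fixed only if the model fails to converge.
- Step 3 of 6.11.5 is headed as an analysis of imputed data but reads `tss`, not the `outm1` written by Step 2, and it has no `BY _imputation_`.
- Placebo is coded 0 in Step 2 of 6.11.5 and 1 in 6.11.4. Placebo sorts first either way, so this does not move the contrast, but Step 2's restriction to code 0 would select nobody under the 6.11.4 coding.

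**The case against.** The best defence is that this is offered as sample code and the intent is plain. The endpoint, the summary measure, the table title and the ESTIMATE's own label all say Weeks 23-24. SAP 4.2.6 makes the summary measure a difference of least squares means, and the `LSMEANS` statement prints exactly that. The code cannot run as printed because of `B_TTS`, so a programmer must edit it anyway. SAP section 7 requires tables to be independently reprogrammed with matching results. In 6.11.5 the misspelling and the wrong input data set also stop the wrong contrast from reaching the pooling step as printed. Finally, the text was read from a PDF by machine, and one lost zero would explain the count.

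Most of this stands, and it is why the point concerns code and not the estimand. Three things remain. SAP 4.2.6 names the quantity but not the output row for the p-value. Independent programming protects less well if both programmers copy the same SAP line. A zero lost in PDF reading cannot be fully excluded, but the same 11 + 12 pattern appears in two separate blocks; a look at the source file would settle it. The probabilities above depend on the wrong row being used, and they say nothing about how likely that is.

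**Conclusion.** The point holds. As printed, the ESTIMATE in SAP 6.11.4 and in Step 3 of 6.11.5 gives the treatment difference at Weeks 21-22 under a Weeks 23-24 label. The governing text is clear, so the estimand has not changed and the practical risk is limited.

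If the wrong row were reported, the estimate would typically shift by 0.88-2.17 points (one SD) against a standard error of 2.80. The significance call would differ with probability 8-20% at 7.4 points, 10-25% at 5.5 points and 3-7% under no effect. With equal true effects in the two windows this is noise and not bias, and it falls equally in both directions. The ranges rest on an assumed correlation of 0.7-0.95 and on an SD of 12.5 with no further reduction for baseline adjustment.

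The wrong contrast would reach the pooled result of the first sensitivity analysis only if the other faults in that code were repaired and the coefficients left alone. It should be corrected because the test gates all the secondary endpoints.

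**What to change.** In SAP 6.11.4 and in Step 3 of 6.11.5, use 24 interaction coefficients: eleven 0s, -1, eleven 0s, 1. Alternatively, state that the Weeks 23-24 difference from `LSMEANS` is the primary result, delete the ESTIMATE, and have Step 4 pool that difference.

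At the same time:

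- In both blocks, change `B_TTS` to `B_TSS` and remove `ANALYSIS_CENTER` from MODEL, keeping the fixed-effect version only as the stated fallback.
- In 6.11.5, make Step 3 read `outm1`, reshaped to the model's long format, by `_imputation_`, and output the contrast for each imputation to Step 4.
- Use one placebo code throughout.

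The cost is a correction to the SAP's sample code before database lock. It needs no new data and changes neither the estimand nor the analysis prose.

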### 6.11.5 Sensitivity Analyses of the Second Co-Primary Endpoint

The two sensitivity analyses planned below are constructed based on the already imputed biweekly data set from Section 5.4.2.

The first sensitivity analysis is based on the placebo-based pattern-mixture model for the missing data imputation under the missing not at random (MNAR) assumption. In this model, subjects from the active treatment group after the ICE are assumed to behave like the subjects from the placebo group. Their missing data are imputed using the response profile from the placebo subjects who have similar baseline covariates and prior response trajectory. The sample SAS code follows.

```

/*Step 1: Achieve Monotone Missing Data Pattern */

proc mi data=tss seed=135791 nimpute=50 out=mono;
  var B_EOS B_TSS TSS_W01_02 TSS_W03_04 ... TSS_W21_22
  TSS_W23_24;
  MCMC impute=monotone nbiter=200 niter=100;
  By TRTMT;
run;

/*Step 2: Achieve Control-Based Copy-Reference Imputation */

proc mi data=mono seed=135791 nimpute=50 out=outm1;
  class TRTMT;
  by _imputation_;
  var TRTMT B_EOS B_TSS TSS_W01_02 TSS_W03_04 ... TSS_W21_22
  TSS_W23_24;

```

```

monotone reg;
mnar model(TSS_W01_02 TSS_W03_04 ... TSS_W21_22 TSS_W23_24 /
modelobs=(TRTMT='0')); * CODE 0 IS FOR PLACEBO GROUP ;
run ;

/*Step 3: Run MMRM Analysis on Imputed Data */

proc mixed data=tss method=reml;
class TRTMT USUBJID AVISITN ANALYSIS_CENTER GENDER;
model CHG= B_TSS TRTMT AVISITN ANALYSIS_CENTER GENDER
TRTMT*AVISITN B_TTS*AVISITN / DDFM=KR;
REPEATED AVISITN / SUBJECT=USUBJID (TRTMT) TYPE=UN;
RANDOM ANALYSIS_CENTER;
LSMEANS TRTMT*AVISITN / PDIFF CL;
ESTIMATE 'PBO VS. AK002 at WEEKS 23-24' TRTMT -1 1
TRTMT*AVISITN 0 0 0 0 0 0 0 0 0 0 -1
0 0 0 0 0 0 0 0 0 0 0 1 / CL;
ODS OUTPUT PARAMETERESTIMATES=PESTIMATES;
RUN;

/*Step 4: Combining estimates from each imputed data set */

proc mianalyze data=PESTIMATES;
modeleffects ESTIMATE;
stderr stderr;
by label;
ods output PARAMETERESTIMATES=miparm;
run ;

```

The second sensitivity analysis is based on ANCOVA using the imputed data set (Section 5.4.2). The LS mean, SE, and 95% CI for each treatment group and for the between group difference will be derived from ANCOVA with treatment as factor, baseline PRO TSS (continuous) as covariates. The hypothesis test for the treatment effect will be carried out by the F-test. The synthesizing method will be used to combine the results from multiple imputations. The sample SAS code follows.

```

/** ANCOVA by imputation **/
ods output diff=diffs lsmeans=lsm;
proc mixed data=ADIMP1 method=reml;
where PARAMCD='TSS6' and ATPT='Weeks 23-24';
by IMPUTED1;
class gender analysis_center TRT01P;
model CHG=gender analysis_center BASE TRT01P;
lsmeans TRT01P / diff;
quit;
ods output close;

```

```
/** Combine LS Means (by treatment and difference) **/
data lsmdiff;
  set lsm_diffs(in=d);
  if d then trt01p='DIFF';
run;

proc sort;
  by trt01p;
run;

/** Synthesized results **/
ods output ParameterEstimates=SYNDIF;
proc mianalyze data=LSMDIFF alpha=0.05;
  by trt01p;
  modeleffects ESTIMATE;
  stderr STDERR;
run;

ods output close;
```

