second co-primary endpoint is confounded by the influence of background variables, then the second co-primary analysis will be conducted adjusting for the effects of the background variables. Possible confounding factors may include age, presence of esophageal inflammation, history of IBS, and presence of diarrhea at baseline.

Two sensitivity analyses are planned. The first is a pattern-mixture model, where it will be assumed that AK002 patients who experience an ICE will have a trajectory comparable to placebo post-ICE. This analysis will therefore provide a stress test of the missing at random (MAR) assumption of the MMRM employed in the principal analysis and will provide a conservative estimate of the treatment effect. The pattern-mixture model will be implemented using multiple imputations, and the inference of this sensitivity analysis will be based on the combined estimates using the standard multiple imputation technique. The imputed data sets will be analyzed with the same MMRM model utilized in the primary analysis and then summarized using PROC MIANALZE. The other is to analyze the average of Week 23 through Week 24 using ANCOVA with treatment and study site as factors, gender and baseline TSS (continuous) as covariates. Missing Week 23 through Week 24 weekly TSS will be imputed prior to ANCOVA using SAS PROC MI under the MAR assumption.

Detailed specifications for the missing data imputation will be provided in the SAP.

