#### 5.4.2 Missing Daily PRO Scores at Weeks 23–24

PRO daily scores will be set to missing if they are collected after subjects have experienced ICE. We note that the day before and day of colonoscopy will be taken into consideration when computing baseline and Week 24 TSS scores. For the endpoints of change in the weekly average of PRO TSS, when  $\geq 4$  of 7 daily scores are available, the weekly average score will be calculated using the available daily scores. (See [Appendix 1](#) for justification of allowing weekly

average being calculated from  $\geq 4$  daily scores.) This calculation implies the missing daily scores are the same as the mean of the non-missing daily scores. When  $\geq 4$  daily scores are missing, the weekly score will be set to missing. For the calculation of the average PRO TSS over Weeks 23–24, if  $\geq 1$  weekly score is missing, the biweekly average of Weeks 23–24 will be considered missing.

Missing average of Weeks 23–24 TSS will be imputed using the Markov Chain Monte Carlo (MCMC) method. Baseline tissue eosinophil count and PRO TSS will be included along with the average biweekly PRO TSS (W01\_02, W03\_04, W05\_06, ..., W21\_22, W23\_24) in the multivariate distribution construction. The imputation will be carried out for each treatment group separately and will be executed multiple (50) times (MI). The purpose of MI is to account for the imputation variability in the parameter estimates. An example of the SAS code for this imputation follows.

```
proc mi data=TSS seed=1357986420 nimpute=50
  out=TSS_IMMPUTED ;
  by TRTMT ;
  mcmc chain=multiple impute=full initial=em nbiter=200 niter=100 ;
  var B_EOS B_TSS TSS_W01_02 TSS_W03_04
  ... TSS_W21_22 TSS_W23_24 ;
  run ;
```

After the imputation, the least squares mean (LSM) and standard error (SE) are derived from the conventional ANCOVA from each imputed data set.

These LSM and SE are synthesized to derive the imputation variability-adjusted LSM and SE for each treatment group and for the between treatment difference. These synthesized LSM and SE are then used in the hypothesis test for the between treatment difference. An example of the SAS code for the synthesized LSM comparisons between treatment is as follows.

```
ods output ParameterEstimates=LSMDIF ;
proc mianalyze data=DIFF alpha=0.05 ;
 modeleffects LSM ;
  stderr SE ;
run ;
```

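### As written, the placebo-based sensitivity analysis of TSS in SAP 6.11.5 does not stress the missing-at-random assumption

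*SAP*

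**What the plan says.** Protocol 15.6.1 sets the aim. AK002 patients with an ICE are taken to follow a placebo-like course afterwards, and "This analysis will therefore provide a stress test of the missing at random (MAR) assumption" behind the primary MMRM. It adds: "The imputed data sets will be analyzed with the same MMRM model utilized in the primary analysis".

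SAP 6.11.5 repeats the aim: "subjects from the active treatment group after the ICE are assumed to behave like the subjects from the placebo group". But it opens with a statement about starting data that covers both sensitivity analyses: "The two sensitivity analyses planned below are constructed based on the already imputed biweekly data set from Section 5.4.2".

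SAP 5.4.2 describes that data set. Daily scores after an ICE are set to missing. Then "The imputation will be carried out for each treatment group separately", 50 times, by MCMC with the option `impute=full` over baseline and all the biweekly TSS variables. Section 5.4.2 does not call this MAR, but Protocol 15.6.1 does when it describes the PROC MI step before the ANCOVA.

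The sample code in 6.11.5 has four steps. Step 1 makes the missingness monotone, Step 2 imputes from placebo, Step 3 fits the MMRM and Step 4 pools. Step 2 identifies placebo by "modelobs=(TRTMT='0')); * CODE 0 IS FOR PLACEBO GROUP", whereas SAP 6.11.4 defines the same variable as "planned treatment group in numeric (1 = placebo, 2 = AK002". Step 3 begins "proc mixed data=tss method=reml".

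**The concern.** A placebo-based imputation can change the result only if the AK002 post-ICE values are still missing when it runs, and only if the analysis model then reads what it produced. The text of 6.11.5 breaks the first condition and the code breaks the second.

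The primary TSS analysis depends on MAR for every subject with an ICE, and this is the only analysis with a stated method that departs from it. The second sensitivity analysis is itself MAR. A tipping point plot appears as Figure 2 in SAP Appendix 3, but no method for it is given. If the plan were followed as written, a sensitivity result close to the primary one could be reported as evidence of robustness when no stress had been applied.

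**Working it through.** **1. The text route.** Under SAP 5.4.2, an AK002 subject's post-ICE scores become missing and are then filled from a model fitted to AK002 subjects only. With `impute=full`, nothing stays missing. If 6.11.5 starts from this output, the placebo model has zero values to impute and the estimate equals the within-arm MAR estimate exactly.

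**2. The code route.**

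| Step in 6.11.5 | Reads | Writes | Comment |
|---|---|---|---|
| 1, monotone MCMC by arm | `tss` | `mono` (50 sets) | not the 5.4.2 output, which has another name |
| 2, copy-reference from placebo | `mono` | `outm1` | only data set with placebo-based values |
| 3, MMRM | `tss` | one set of estimates | no BY `_imputation_`; `outm1` not read |
| 4, pooling | Step 3 estimates | pooled result | no per-imputation estimates to pool |

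Step 3 is headed as an analysis of imputed data, but apart from an output line it repeats the primary MMRM code of 6.11.4. Text and code also name different starting data, so correcting one does not correct the other.

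The same block has further faults:
- Placebo is taken as code 0, where 6.11.4 uses 1.
- Step 2 requests 50 imputations within each of the 50 Step 1 sets, giving 50 × 50 = 2,500.
- No step turns `outm1` into one row per visit or recalculates the change score. Appendix 4 does recalculate it for the ANCOVA.
- `B_TTS` stands where `B_TSS` is meant.

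**3. What a working analysis would do.** The plan gives no figure for this, so the size rests on assumptions. From SAP 3.5: effect 7.4, SD 12.5, 40 per arm. Assumed: a proportion p of AK002 subjects with an ICE (none on placebo), an effect constant over time, and AR(1) correlation ρ between adjacent biweekly visits of 0.7 to 0.9.

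Under copy-reference, an AK002 subject's last pre-ICE value lies on average 7.4 points from the placebo mean. The placebo regression carries forward ρ^k of that advantage over k visits, so

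shift towards zero = p × 7.4 × (1 − ρ^k).

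Weeks 23–24 is biweekly visit 12. Last data at Weeks 5–6, 11–12 or 19–20 (visits 3, 6, 10) give k = 9, 6 or 2. Example: 0.30 × 7.4 × (1 − 0.7^9) = 0.30 × 7.4 × 0.960 = 2.13.

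| Last pre-ICE data | ρ | p = 10% | 20% | 30% |
|---|---|---|---|---|
| Weeks 5–6 | 0.7 | 0.71 | 1.42 | 2.13 |
| Weeks 5–6 | 0.9 | 0.45 | 0.91 | 1.36 |
| Weeks 11–12 | 0.7 | 0.65 | 1.31 | 1.96 |
| Weeks 11–12 | 0.9 | 0.35 | 0.69 | 1.04 |
| Weeks 19–20 | 0.7 | 0.38 | 0.75 | 1.13 |
| Weeks 19–20 | 0.9 | 0.14 | 0.28 | 0.42 |

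The late row matters because several ICEs in SAP Appendix 2 depend on medication use in, or continuing into, Weeks 21–24.

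**4. Checks.** A simulation (1,500 replicates, 40 per arm) gave copy-reference minus within-arm MAR differences, for p = 10/20/30%, of:
- Weeks 5–6: 0.70/1.42/2.22 (ρ = 0.7) and 0.46/0.90/1.35 (ρ = 0.9)
- Weeks 19–20: 0.39/0.75/1.20 and 0.15/0.28/0.44

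The Weeks 11–12 rows rest on the formula alone. Within-arm MAR estimates averaged −7.23 to −7.54, against a true −7.4. A separate large-sample simulation, with ICEs in both arms at 5% to 30% and an effect that builds up over the first visits, gave 0.2 to 1.5 points of attenuation. In it, the literal text route reproduced the MAR estimate in every case.

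**5. Scale.** SE of the difference = 12.5 × √(2/40) = 2.80. An estimate of 7.4 loses two-sided significance at 5% if it shrinks by more than 7.4 − 1.96 × 2.80 ≈ 1.9 points. Two of the 18 cells exceed that, both at 30% ICE and ρ = 0.7.

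**The case against.** The strongest reply is that this is loose drafting and that the analysis is not really absent. The intent is stated in the narrative of 6.11.5, the headings of Steps 3 and 4, the title of Table 14.2.2.2 and the protocol. The code is labelled as a sample, and `tss` must be a placeholder, since it is wide in Step 1 and long in Step 3. The code could not run unedited, and SAP 7 requires independent reprogramming, so a silent error is unlikely. The `B_TTS` slip also occurs in the primary code. The analysis lies outside the testing hierarchy in SAP 5.8. Subjects with an ICE count as non-responders for the binary TSS endpoints, so those do not lean on MAR for ICEs.

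Most of this stands, and it limits the severity. It does not remove the fault. The sentence about starting data is SAP narrative, and both documents say that the SAP's statistical methods supersede the protocol's. Two programmers working independently from a self-contradictory text could agree on the wrong reading. The binary endpoints are different endpoints and do not test the MMRM's assumption.

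The sizes are wholly assumption-driven, and the larger ones need frequent, early ICEs. At 10% or 20% ICE, no cell would overturn a result of exactly 7.4 points.

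**Conclusion.** The concern holds. Followed literally, the text yields a within-arm MAR result. The code yields either the primary MMRM again or a program that does not run. The placebo-based stress test promised in Protocol 15.6.1 is therefore not delivered, and no other MNAR analysis has a stated method.

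That conclusion follows from reading the two SAP sections and needs no assumption. Its size does. For 10% to 30% ICE in the AK002 arm, the attenuation that would go unseen is about 0.3 to 2.1 points if data end at Weeks 5–6 to 11–12, and about 0.1 to 1.1 points if they end at Weeks 19–20. Most of this is well below one standard error, but it could matter for a borderline result. The primary estimate and the formal tests are not affected. This should be fixed, but it does not undermine the trial.

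**What to change.** Before unblinding, amend SAP 6.11.5:

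1. Restrict the opening sentence on starting data to the ANCOVA analysis. State that the placebo-based analysis starts from unimputed biweekly TSS with post-ICE values missing.
2. Step 1: monotone MCMC by arm, 50 data sets.
3. Step 2: one imputation per data set (`nimpute=1`), with `MODELOBS` set to the actual placebo code. Use one treatment coding throughout the SAP.
4. Reshape `outm1` to one row per visit and recalculate change from baseline.
5. Step 3: fit the MMRM to that data set BY `_imputation_`, with `B_TTS` corrected to `B_TSS`, and output the Weeks 23–24 contrast.
6. Step 4: pool the 50 estimates.
7. Either describe the tipping point analysis or remove Figure 2 from Appendix 3.

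The cost is SAP wording and code only; conduct and data collection do not change. The sponsor should accept that the resulting estimate may look less favourable than the MAR one.
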